I have read this protocol and agree to adhere to, the protocol, the local IRB/IEC regulatory requirements and the ICH Harmonised Guideline Integrated Addendum To ICH E6(R1): Guideline For Good Clinical Practice: E6(R2)

I will provide copies of this study protocol and all necessary information about this study to the study staff under my supervision.

I will discuss this material with them and ensure they are fully informed about the device under investigation as well as the aspect concerning the conduct of the study.

Investigator	
Name:	_____
Institution:	_____
Address:	_____
Phone:	_____
Email:	_____
Signature:	_____
Date:	_____

PROTOCOL SYNOPSIS

Title	Incision Management with Prevena After Renal Transplant (IMPART-TRIAL)
Objectives	
Primary: The primary objective of this study is to determine if the Prevena Incision Management System reduces wound complications at the surgical site following renal transplant, when compared to standard dressings.
 
Secondary: Secondary objectives of this study include identification of risk factors for wound complications at the surgical site, as well as reoperation, prolonged hospital stay, allograft survival, delayed graft function. This study will also assess pain, scar healing and quality of life in each treatment arm, and aim to complete a cost-benefit analysis of the Prevena device in renal transplantation.

Study Design	This study is a multicentre, partially-blinded randomised controlled trial, with site stratified block randomisation and partial blinding of outcome assessments. Patients undergoing a renal transplant will be allocated to one of two treatment arms, where either a Prevena device of appropriate size or standard dressing is applied to the closed incision. In the case that a patient requires bilateral incisions, both incisions will be allocated to the same treatment arm and counted as a single incision.
Planned Sample Size	250 participants each arm (500 total)
Selection Criteria	All patients presenting for a renal transplant over a 24 month period at one of the participating sites will be eligible for enrolment in this study. Only participants who give informed consent will be enrolled in the study.
Study Procedures	Participants will be randomised to either a Prevena (intervention arm) or standard dressing (control arm) is placed on the closed incision after renal transplantation. Monitoring will occur daily during hospitalization and up to 30 days postoperatively to review any wound complications, with subsequent assessment at 90 days.
Statistical Procedures and Analysis Plan:	Statistical analysis will be pre-specified and conducted according to both principles of intention of treat and per-protocol analysis, using SPSS version 20 (IBM, Armonk, NY, USA). The Intention to Treat (ITT) sample will be based on all enrolled subjects, and the per-protocol analysis will be based on all patients who have a dressing placed on the closed incision following renal transplant. Each incision will be randomized to the Prevena or standard dressing group. In the case that a patient requires bilateral incisions, both incisions will be allocated to the same treatment arm and counted as a single incision. Baseline characteristics of the two groups will be recorded and compared using Student's t-test and chi-square test for continuous and discrete data respectively. The primary outcome, the proportion of wound complications, will be compared between the Prevena and standard dressing groups using a chi-square test without Yates' continuity correction with a two-sided alpha of 0.05 at the final analysis using the Peto approach to preserve the overall

	
significance level of 0.05 (23). Patients lost to follow-up will be used in an intention-to-treat analysis with last observation carried forward
 
The secondary outcome of identification of risk factors for wound complications will be assessed by multiple logistic regression of collected variables to assess their odds ratio.

Sample Size Calculation:	
Wound infection rates have been estimated between 5 and 30% based on current literature, including a systematic review and meta-analysis.(3)(10) Weighting the participating site’s preliminary audit data by expected enrolment rates, the average wound complication rate was estimated to be 15%. NPWT has been suggested to offer an approximate 46% reduction in wound infection rates for abdominal incisions (3)(10). Based on a type one two-sided error of $\alpha = 0.05$ and a type two error of $\beta = 0.2$ (corresponding to a power of 80%) a total sample size of 239 patients per group (478 in total) is needed to evaluate primary endpoints, which was calculated using the power formula for a chi-square test without Yates’ continuity correction due to the large sample size and binary dependent variable (17). Accounting for potential loss to follow up, the sample size has been rounded up to 250 per arm (500 total).

Duration of the study	24 months

GLOSSARY OF ABBREVIATIONS

ABBREVIATION	TERM
CNC	Clinical Nurse Consultant
NPWT	Negative Pressure Wound Therapy
Prevena	PREVENA Incision Management System
SD	Standard (waterproof, adhesive) Dressings
RT	Renal Transplant
RNSH	Royal North Shore Hospital; Sydney, Australia
RPAH	Royal Prince Alfred Hospital; Sydney, Australia
WH	Westmead Hospital; Sydney, Australia
HD	Haemodialysis
PD	Peritoneal dialysis
LOS	Length Of Stay
EC	Ethics Committee
PISCF	Patient Information Sheet and Consent Form
ITT	Intention to Treat
IFU	Instructions for Use
EQ-5D-5L	A Quality of life standardised instrument developed by the EuroQol Group
NRS	Numerical Rating Scale
POSAS	The Patient and Observer Scar Assessment Scale
MCS	Microscopy, Culture and Sensitivity
REDCap	Research Electronic Data Capture

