4.6 Primary and Secondary Outcome Measures

Primary outcomes of this study include wound infection, wound dehiscence or fluid collection at the surgical site within 30 postoperative days (see Appendix for Classification of wound complications)

Secondary outcomes include pain, scar healing, quality of life, reoperation, duration and volume of wound drainage, graft function, hospital length of stay, clinical adverse events and mortality (see Appendix for NRS, POSAS, EQ 5D-5L and List of dependent variables).

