5.6 Participant Withdrawal

5.6.1 Reasons for withdrawal

Patients may withdraw from the study at any point, but will continue to be followed up and managed as per routine practice. Patient withdrawal may also occur due to loss of follow up, adverse event or death. Investigators may withdraw the patient from the study once the patient has been randomised, if the Investigator believes the allocated treatment arm is not in the patient's best interests, or the patient meets IFU related contraindications, however the reasons for withdrawal must be clearly documented.

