5.6.2 Handling of withdrawals

[figure not shown]
All participants withdrawn will ideally complete all study visits including Day 30 follow-up if able, as per routine clinical practice. Withdrawn patients will be included in an intention to treat analysis.

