6 STUDY VISITS AND PROCEDURES SCHEDULE

Study Flow Chart

Timeline for follow up wound assessments:

Day 7 – The dressing is taken down for review and not replaced unless indicated. The review will include a microbiology swab (MCS); photo of the wound; modified ASEPSIS wound assessment; a pain assessment (NRS) and patient quality of life questionnaire (EQ-5D).

Day 14 – The dressing is taken down for review and not replaced unless indicated. The review will include a microbiology swab (MCS); photo of the wound; modified ASEPSIS wound assessment; a pain assessment (NRS) and the quality of life questionnaire (EQ-5D).

Day 30 (+/- 3 days) – The patient will present for follow up for an extended wound review by a study clinician or wound CNC, and a vascular sonographer. The review will include a modified ASEPSIS wound assessment; a photo of the wound; a pain and scar assessment (POSAS); a quality of life questionnaire (EQ-5D) and an ultrasound of the transplanted kidney which will also identify deep wound complications.

Day 90 (+/- 3 days) – The patient will present for follow up for wound review and ultrasound, which will include a photo of the wound; a scar assessment (POSAS); a quality of life questionnaire (EQ-5D) and an ultrasound of the transplanted kidney which will also identify deep wound complications.

Event	Day 0 Enrolment	Day 7	Day 14	Day 30 (+/- 3 days)	Day 90 (+/- 3 days)
Screening for Inclusion / Exclusion criteria	✓				
Participant Information Sheet and Consent Form (PISCF)	✓				
Routine perioperative data collection (Appendix C)	✓	✓	✓	✓	✓
Modified ASEPSIS wound assessment (Appendix B)		✓	✓	✓	✓
Photo of wound using REDCap App		✓	✓	✓	✓
Quality of life questionnaire (EQ-5D-5L) (Appendix D)		✓	✓	✓	✓
Microbiology swab (MCS)		✓	✓		
Pain Assessment (NRS) (Appendix G)		✓	✓		
Pain and Scar Assessment (POSAS) (Appendix E, F)				✓	✓
Ultrasound of Transplanted Kidney (Study specific)				✓	✓
Adverse Event & Serious Adverse Event Assessment		✓	✓	✓	✓

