9 STATISTICAL METHODS

9.1 Sample Size Estimation

Wound infection rate have been estimated between 5 and 30% based on a current literature, including a systematic review and meta-analysis.(3)(10) Weighting the participating site's preliminary audit data by expected enrolment rates, the average wound complication rate was estimated to be 15%. NPWT has been suggested to offer an approximate 46% reduction in wound infection rates for abdominal incisions (3)(10).

Based on a two-sided type one error of $\alpha = 0.05$ and a type two error of $\beta = 0.2$ (corresponding to a power of 80%) a total sample size of 239 patients per group (478 in total) is needed to evaluate primary

endpoints, which was calculated using the power formula for a chi-square test without Yates' continuity correction due to the large sample size and binary dependent variable (22). Accounting for potential loss to follow up, which is estimated to be minimal, as every patient receiving a kidney transplant is planned to follow up every day for 30 days postoperatively, the sample size has been rounded up to 250 per arm (500 total). Missing data from patients who fail to have endpoints recorded will be treated on an intention to treat basis with last observation carried forward.

Estimated mean wound complication rate in control arm across 3 sites : 15%

Site 1 : 5-10% (60 transplants per year, audit data demonstrates 5% dehiscence rate)

Site 2 : 8-15% (90 transplants per year, audit data demonstrates 8% infection rate)

Site 3 : 18-25% (100 transplants per year, audit data demonstrates 18% dehiscence rate)

Conservative estimate of treatment effect: ~50% reduction in all wound complications with closed incision NPWT over lower abdominal/groin wounds (Rutherford Morrison) in high risk population.

Estimated complication rate for Prevena arm (intervention) = 7%

Dichotomous Endpoint, Two Independent Sample Study

Sample Size	
Group 1	239
Group 2	239
Total	478

Study Parameters	
Incidence, group 1	15%
Incidence, group 2	7%
Alpha	0.05
Beta	0.2
Power	0.8

$$N_1 = \left\{ z_{1-\alpha/2} * \sqrt{\bar{p} * \bar{q} * \left(1 + \frac{1}{k}\right)} + z_{1-\beta} * \sqrt{p_1 * q_1 + \left(\frac{p_2 * q_2}{k}\right)} \right\}^2 / \Delta^2$$

$$q_1 = 1 - p_1$$

$$q_2 = 1 - p_2$$

$$\bar{p} = \frac{p_1 + k p_2}{1 + K}$$

$$\bar{q} = 1 - \bar{p}$$

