9.3 Statistical Analysis Plan

Statistical analysis will be pre-specified and conducted according to both principles of intention to treat and per-protocol analysis, using SPSS version 20 (IBM, Armonk, NY, USA). Each incision will be randomized to the Prevena or standard dressing group. In the case that a patient requires bilateral incisions, both incisions will be allocated to the same treatment arm and counted as a single incision. Baseline characteristics of the two groups will be recorded and compared using Student's t-test and chi-square test for continuous and discrete data respectively. The primary outcome, the proportion of wound complications, will be compared between the Prevena and standard dressing groups using a chi-square test without Yates' continuity correction with a two-sided alpha of 0.05 at the final analysis using the Peto approach to preserve the overall significance level of 0.05 (23). An absolute risk increase/reduction for wound complications will be presented for the use of Prevena, as well as the number needed to treat in order to prevent specific wound complications. Patients lost to follow-up will be used in an intention-to-treat analysis with last observation carried forward.

The secondary outcome of identification of risk factors for wound complications will be assessed by multiple logistic regression of collected variables to assess their odds ratio. To prevent overfitting with the selected sample size, variables will be stepwise selected and also assessed for multicollinearity with the significance level of the dependent variables adjusted for multiplicity. Secondary outcomes will be compared between groups using a chi-square or Fisher's test for reoperation rate and delayed graft function and t-test for continuous variables, including the pain scale and quality of life. Non-normally distributed continuous variables will be tested for and compared using the Mann-Whitney *U* test. Survival analysis will be performed for allograft survival time with subjects without events censored at the 90 day final observation. A *p* value of less than 0.05 will be considered significant for the secondary outcomes and all tests will be two-sided.

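### Last observation carried forward is the only missing-data rule and is not limited to the primary outcome, so early EQ-5D-5L, pain and scar scores can stand in for later visits; death is not addressed

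*Combined protocol and SAP*

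**What the plan says.** The rule appears three times in the combined protocol and SAP. The synopsis (statistical procedures) and Section 9.3 use the same sentence: "Patients lost to follow-up will be used in an intention-to-treat analysis with last observation carried forward". Section 9.1 is wider: "Missing data from patients who fail to have endpoints recorded will be treated on an intention to treat basis with last observation carried forward". None of the three names the endpoints covered, excludes any, or mentions death.

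On withdrawal, Section 5.6.1 says "Patient withdrawal may also occur due to loss of follow up, adverse event or death", and Section 5.6.2 says "Withdrawn patients will be included in an intention to treat analysis".

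On analysis, Section 9.3 plans a "t-test for continuous variables, including the pain scale and quality of life", with Mann-Whitney for non-normal data. It names no visit and no repeated-measures model. One secondary endpoint has its own rule: "Survival analysis will be performed for allograft survival time with subjects without events censored at the 90 day final observation". Section 4.6 lists "hospital length of stay, clinical adverse events and mortality" among the secondary outcomes, so deaths are counted, but their effect on the patient-reported scores is not defined.

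The schedule in Section 6 has EQ-5D-5L at Days 7, 14, 30 and 90, NRS at Days 7 and 14, and POSAS at Days 30 and 90. There is no Day 0 score on any of them.

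**The concern.** Quality of life, pain and scar healing are stated secondary objectives (Section 3.2). They can be expected to change as patients recover from surgery and as scars mature. A carried score freezes a patient at an earlier stage of recovery. If more patients leave one arm, or leave it earlier, that arm looks worse (or, for a dead patient, better) for reasons unrelated to the dressing. The filled-in values also enter the t-test as if observed, so the standard error ignores that they are missing.

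Unequal loss is plausible here. Patients and clinical staff are unblinded (Section 5.4). Investigators may withdraw a randomised patient because of the allocated arm or a contraindication in the device instructions (Section 5.6.1). The argument in Section 9.1 that loss will be small rests on daily contact for 30 days, whereas EQ-5D-5L and POSAS run to Day 90.

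**Working it through.** **Plan's own figure.** With 15% v 7%, two-sided alpha 0.05 and 80% power, the formula printed in Section 9.1 gives (1.96·√(0.11·0.89·2) + 0.84·√(0.15·0.85 + 0.07·0.93))² / 0.08² = 238.7, so 239 per group. This reproduces, and nothing below alters it. Rounding 239 up to 250 implies a loss allowance of 11/250 = 4.4% per arm. If the allowance for both arms fell in one arm, that would be 22/250 = 8.8%.

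**What the schedule allows to be carried.**

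| Scale | Visits | Possible carry-forward |
|---|---|---|
| EQ-5D-5L | 7, 14, 30, 90 | Day 7, 14 or 30 to Day 90 (and to visits between) |
| NRS | 7, 14 | Day 7 to Day 14 only |
| POSAS | 30, 90 | Day 30 to Day 90 only |

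**Size for EQ-5D at Day 90.** The documents give no EQ-5D values, loss rates or death rates. Assumptions: means 0.60, 0.68, 0.78 and 0.84 at the four visits, SD 0.20, within-patient correlation 0.6, 250 per arm, no true difference.

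- Bias = (difference in missing share) × (0.84 − mean at last visit).
- Standard error of the difference = 0.20·√(2/250) = 0.0179.
- With z = bias/SE, the false-positive rate is approximately Φ(−1.96 + z) + Φ(−1.96 − z).

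| Missing | Last seen | Bias | z | False-positive rate |
|---|---|---|---|---|
| 2% v 7% | Day 30 | 0.05 × 0.06 = 0.003 | 0.17 | about 5% |
| 2% v 7% | Day 14 | 0.05 × 0.16 = 0.008 | 0.45 | about 7% |
| 2% v 7% | Day 7 | 0.05 × 0.24 = 0.012 | 0.67 | about 10% |
| 0% v 8.8% | Day 30 | 0.088 × 0.06 = 0.005 | 0.30 | about 6% |
| 0% v 8.8% | Day 14 | 0.088 × 0.16 = 0.014 | 0.79 | about 12% |
| 0% v 8.8% | Day 7 | 0.088 × 0.24 = 0.021 | 1.18 | about 20% |
| equal | any | 0 | 0 | 5% |

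Simulating trials under the same assumptions agrees with these rates to within about one to two percentage points.

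**Death.** Carrying 0.68 instead of scoring 0 raises an arm mean by 0.68/250 = 0.0027 per death, or 0.15 standard errors. For 1 to 11 deaths in an arm (0.4% to 4.4%) and a carried score of 0.5 to 0.9, the arm mean is overstated by 0.002 (0.004 × 0.5) to 0.040 (0.044 × 0.9). The bias between arms is the difference between the two arms' shifts. A patient who dies before the Day 7 assessment has no score to carry.

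**The case against.** The strongest reply is that the rule may be meant for the primary outcome only. In the synopsis and Section 9.3 it closes the primary-outcome text, and in Section 9.1 it sits in a sample-size section about the primary endpoint. That reading is possible, so a reader who infers that carry-forward covers every endpoint goes too far; allograft survival is explicitly censored instead. But the narrow reading leaves EQ-5D-5L, NRS and POSAS with no missing-data rule at all, in a plan described as pre-specified. Either way the text needs the same correction.

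A reader might also infer that scar scores from the first weeks replace Day 90 scores, or that early pain scores run to Day 90. The schedule rules out both: POSAS starts at Day 30 and NRS ends at Day 14.

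Nor do the documents state that a dead patient keeps a living score. The sentence in the synopsis covers loss to follow-up, which Section 5.6.1 lists separately from death. The result needs Sections 5.6.1, 5.6.2 and 9.1 read together. It is permitted, not prescribed.

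On size, the objection largely stands. Given daily contact to Day 30, the likeliest last score before a missed Day 90 visit is Day 30, where the bias is only 0.003 to 0.005. The higher rates need early and one-sided loss. It is also fair that a mixed model implicitly extrapolates past death, and that a utility of 0 at death is one choice among several for the quality-of-life comparison.

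**Conclusion.** The point holds as a gap in the secondary analyses. Carry-forward is the only missing-data rule, its widest statement has no endpoint limit, and nothing says how death enters the quality-of-life comparison. The likely effect is small if loss is low, balanced or late: at most 0.3 standard errors when patients are last seen at Day 30. It reaches 0.8 to 1.2 standard errors only if all loss falls in one arm by Day 14. These sizes rest wholly on the assumed EQ-5D path and loss rates. The primary analysis and sample size are not touched by this point. The change is worth making because it is cheap and uses data already planned.

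**What to change.** In Sections 9.1 and 9.3 and the synopsis, state which endpoints carry-forward covers, and that it is not used for EQ-5D-5L, NRS or POSAS. Analyse the observed visits of each scale with a mixed model for repeated measures (arm, visit, arm by visit, site), and name the visit of main interest.

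Do not carry scores past death. Report deaths by arm beside each scale, set EQ-5D utility to 0 from the date of death in any economic analysis, and state the chosen handling of death for the quality-of-life comparison.

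The cost is SAP wording and one standard model per scale, available in the named software, with no new data. The model assumes data are missing at random, and patients who leave before Day 30 contribute no POSAS data.

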1.5 Sponsor

Northern Sydney Local Health District

1.6 Funding and resources

Internal funding from each centre.

2. INTRODUCTION AND BACKGROUND

2.1 Background Information

Renal transplantation is considered to be the best treatment option for patients with end stage kidney disease in terms of quality of life and survival outcomes, as well as relative cost efficiency compared to dialysis.(1) Transplant recipients are susceptible to wound complications, arguably the most common post-transplant surgical complication, which may contribute to an additional risk of graft rejection or failure, prolonged length of stay, readmission and re-operation, as well as increased treatment costs. (2)

Wound complications have been previously superficial or deep dehiscence and/or infection, perigraft collections or seromas, cellulitis, lymphocoeles, and prolonged wound drainage. Studies have shown that the most important risk factors for wound complications in transplantation are immunosuppression and obesity (3). The incidence of wound infection in the presence of immunosuppression is approximately 7%, and more potent immunosuppressive agents are thought to result in a higher incidence of wound complications. (4) Comparing patients with high (>30) and low BMI (<30) patients, meta-analyses have demonstrated a significantly higher risk of wound infection (RR = 3.13, CI, 2.08–4.71; P <0.001), and wound dehiscence (RR 4.85, CI, 3.25–7.25; P <0.001). (5)(6)

Other relevant factors in renal transplantation include surgical technique and expertise, reoperative procedures, the presence of a haematoma, as well as recipient comorbidities such as advanced age, diabetes, malnutrition, dialysis (haemo- and peritoneal), and prolonged uraemia. The surgical closure technique of the incision, in particular, the precise closure of defects in each layer, has also been identified as an independent factor in reducing wound complications. (7) (8)

Negative pressure wound therapy (NPWT) utilises a foam sponge, in combination with a semipermeable adhesive dressing and a vacuum pump device to increase blood flow, drain fluid and exudate, and contract wound edges. Meta- analyses have suggested that when compared to standard wound dressings on closed incisions, NPWT significantly decreases wound size and healing time, with a significant reduction of risk of surgical site infections (RR=0.54, p= 0.01), and a significant reduction in risk of seroma formation (RR=0.48, p=0.01). (9) (10) (11).

In high risk wounds following cardiac and orthopaedic surgery, NPWT has been used safely without complications. (12) (13) Furthermore, international studies have demonstrated through cost-utility analysis that closed-incision negative-pressure therapy is likely a cost-saving technology when used in high-risk patients following abdominal incisions. (14)

